Appendix 2. Clinical Laboratory Tests

Laboratory Tests

Hematology ^a	Clinical Chemistry ^a
Hematocrit	Sodium
Hemoglobin	Potassium
Erythrocyte count (RBC)	Glucose, random
Mean cell volume	Blood urea nitrogen (BUN)
Mean cell hemoglobin	Total protein
Mean cell hemoglobin concentration	Albumin
Leukocytes (WBC)	Total bilirubin
Cell morphology ^b	Alkaline phosphatase (ALP)
Absolute counts of:	Aspartate aminotransferase (AST)
Neutrophils	Alanine aminotransferase (ALT)
Lymphocytes	Creatinine
Monocytes	Serology ^d
Eosinophils	Hepatitis B surface antigen
Basophils	Hepatitis B core antibody
Platelets	Hepatitis C antibody
Urinalysis ^a	HIV
Specific gravity	Ethanol testing ^e
pH	Urine drug screen ^e
Protein	Serum/urine pregnancy test ^f
Glucose	FSH (females only, to confirm menopausal status) ^d
Ketones	
Bilirubin	
Urobilinogen	
Blood	
Microscopic examination of sediment ^c	

Abbreviations: FSH = follicle-stimulating hormone; HIV = human immunodeficiency virus; RBC = red blood cells; WBC = white blood cells.

- a Results will be validated by the laboratory at the time of initial testing.
- b To be done as needed.
- c Test only if dipstick result is abnormal.
- d Performed at screening only.
- e Urine drug screen and ethanol level will be performed locally at screening and may be repeated prior to admission to the clinical research unit and as indicated.
- f Required for females of child-bearing potential only; however, pregnancy tests carried out in females of non-childbearing pending receipt of FSH results will not be considered a protocol deviation, . Serum pregnancy test will be done at screening, and may be repeated using urine or serum test prior to admission to the clinical research unit and as indicated.

Appendix 3. Study Governance, Regulatory and Ethical Considerations

Informed Consent

The investigator is responsible for:

- Ensuring that the subject understands the potential risks and benefits of participating in the study.
- Ensuring that informed consent is given by each subject or legal representative. This includes obtaining the appropriate signatures and dates on the ICF prior to the performance of any protocol procedures and prior to the administration of investigational product.
- Answering any questions the subject may have throughout the study and sharing in a timely manner any new information that may be relevant to the subject's willingness to continue his or her participation in the trial.

Ethical Review

The investigator must give assurance that the ERB was properly constituted and convened as required by International Council for Harmonisation (ICH) guidelines and other applicable laws and regulations.

Documentation of ERB approval of the protocol and the ICF must be provided to Lilly before the study may begin at the investigative site(s). Lilly or its representatives must approve the ICF before it is used at the investigative site(s). All ICFs must be compliant with the ICH guideline on GCP.

The study site's ERB(s) should be provided with the following:

- the current IB and updates during the course of the study
- ICF
- relevant curricula vitae

Regulatory Considerations

This study will be conducted in accordance with:

- 1) consensus ethics principles derived from international ethics guidelines, including the Declaration of Helsinki and Council for International Organizations of Medical Sciences (CIOMS) International Ethical Guidelines
- 2) applicable ICH GCP Guidelines
- 3) applicable laws and regulations

Some of the obligations of the sponsor will be assigned to a third-party organization.

Protocol Signatures

The sponsor's responsible medical officer will approve the protocol, confirming that, to the best of his or her knowledge, the protocol accurately describes the planned design and conduct of the study.

After reading the protocol, the principal investigator will sign the protocol signature page and send a copy of the signed page to a Lilly representative.

Final Report Signature

The final report coordinating investigator or designee will sign the clinical study report for this study, indicating agreement that, to the best of his or her knowledge, the report accurately describes the conduct and results of the study.

The investigator with the most enrolled subjects will serve as the final report coordinating investigator. If this investigator is unable to fulfill this function, another investigator will be chosen by Lilly to serve as the final report coordinating investigator.

The sponsor's responsible medical officer and statistician will sign/approve the final clinical study report for this study, confirming that, to the best of his or her knowledge, the report accurately describes the conduct and results of the study.

Data Quality Assurance

To ensure accurate, complete, and reliable data, Lilly or its representatives will do the following:

- provide instructional material to the study sites, as appropriate
- provide training to instruct the investigators and study coordinators. This training will give instruction on the protocol, the completion of the eCRFs, and study procedures.
- make periodic visits to the study sites
- be available for consultation and stay in contact with the study site personnel by mail, telephone, and/or fax
- review and evaluate eCRF data and/or use standard computer edits to detect errors in data collection
- conduct a quality review of the database

In addition, Lilly or its representatives will periodically check a sample of the subject data recorded against source documents at the study site. The study may be audited by Lilly and/or regulatory agencies at any time. Investigators will be given notice before an audit occurs.

The investigator will keep records of all original source data. This might include laboratory tests, medical records, and clinical notes. If requested, the investigator will provide the sponsor, applicable regulatory agencies, and applicable ERBs with direct access to the original source documents.

Data Collection Tools/Source Data

An electronic data capture system will be used in this study. The sites must define and retain all source records and must maintain a record of any data where source data are directly entered into the data capture system.

Study and Site Closure***Discontinuation of Study Sites***

Study site participation may be discontinued if Lilly or its designee, the investigator, or the ERB of the study site judges it necessary for medical, safety, regulatory, or other reasons consistent with applicable laws, regulations, and GCP.

Discontinuation of the Study

The study will be discontinued if Lilly or its designee judges it necessary for medical, safety, regulatory, or other reasons consistent with applicable laws, regulations, and GCP.

Appendix 4. Hepatic Monitoring Tests for Treatment-Emergent Abnormality

Selected tests may be obtained in the event of a treatment-emergent hepatic abnormality and may be required in follow-up with subjects in consultation with Lilly Clinical Pharmacology or its designee CRP.

Hepatic Monitoring Tests

Hepatic Hematology^a

Hemoglobin
Hematocrit
RBC
WBC
Neutrophils, segmented
Lymphocytes
Monocytes
Eosinophils
Basophils
Platelets

Hepatic Chemistry^a

Total bilirubin
Conjugated bilirubin
Alkaline phosphatase
ALT
AST
GGT
CPK

Haptoglobin^a

Hepatic Coagulation^a

Prothrombin time
Prothrombin time, INR

Hepatic Serologies^{a,b}

Hepatitis A antibody, total
Hepatitis A antibody, IgM
Hepatitis B surface antigen
Hepatitis B surface antibody
Hepatitis B core antibody
Hepatitis C antibody
Hepatitis E antibody, IgG
Hepatitis E antibody, IgM

Anti-nuclear antibody^a

Anti-smooth muscle antibody (or anti-actin antibody)^a

Abbreviations: ALT = alanine aminotransferase; AST = aspartate aminotransferase; CPK = creatine phosphokinase; GGT = gamma-glutamyl transferase; Ig = immunoglobulin; INR = international normalized ratio; RBC = red blood cells; WBC = white blood cells.

^a Assayed by Lilly-designated or local laboratory.

^b Reflex/confirmation dependent on regulatory requirements and/or testing availability.

Appendix 5. Blood Sampling Summary

This table summarizes the approximate number of venipunctures and blood volumes for all blood sampling (screening, safety laboratories, and bioanalytical assays) during the study. Fewer venipunctures and blood draws may actually occur, but this will not require a protocol amendment.

Protocol I5Q-MC-CGAQ Sampling Summary

Purpose	Maximum Blood Volume per Sample (mL)	Maximum Number of Blood Samples	Maximum Total Volume (mL)
Screening tests ^a	45	1	45
Clinical laboratory tests ^a	9	5	45
LY2951742 pharmacokinetics	2.5	20 ^b	50
Plasma CGRP	8.5	20 ^b	170
Immunogenicity	10	9 ^b	90
Pharmacogenetics	10	1	10
Total			410
Total for clinical purposes [rounded up to nearest 10 mL]			410

^a Additional samples may be drawn if needed for safety purposes.

^b Includes a potential 3 additional samples.

Appendix 6. Injection-Site Reaction Severity Grading Scale

The following table is to be used as a guidance:

Grading^a/ Symptoms	No or Minimal (Grade 0)	Mild (Grade 1)	Moderate (Grade 2)	Severe (Grade 3)
Erythema	0 to <25 mm	25 to 50 mm	51 to 100 mm	>100 mm
Induration	0 to <25 mm	25 to 50 mm and does not interfere with activity	51 to 100 mm or interferes with activity	>100 mm or prevents daily activity
Pain	No to minimal	Mild	Moderate	Severe
Pruritus	No to minimal	Mild	Moderate	Severe

^a The most severe symptom will drive grading.

Leo Document ID = 88d816ca-1ff0-418d-8bdc-68ce1a04fd94

Approver: PPD
Approval Date & Time: 31-May-2016 13:42:09 GMT
Signature meaning: Approved

Approver: PPD
Approval Date & Time: 31-May-2016 15:11:14 GMT
Signature meaning: Approved

## 2. ABBREVIATIONS

Abbreviations pertain to the Statistical Analysis Plan (SAP) only (not the tables, figures and listings [TFLs]).

AE	adverse event
AI	autoinjector
ANOVA	analysis of variance
AUC	area under the concentration versus time curve
AUC(0-∞)	area under the concentration versus time curve from zero to infinity
%AUC(t last -∞)	percent of AUC(0-∞) extrapolated
AUC(0-t last )	area under the concentration versus time curve from time zero to time t, where t is the last time point with a measurable concentration
BQL	below quantifiable limit
C max	maximum observed concentration
CI	confidence interval
CGRP	calcitonin gene-related peptide
CL/F	apparent total body clearance of drug calculated after extra-vascular administration
CRF	Case Report Form
CSR	Clinical Study Report
CRU	Clinical Research Unit
CV	coefficient of variation
EC	Early Clinical
ECG	electrocardiogram
e.g.	For example (Latin: exempli gratia )
ICH	International Council on Harmonisation
LLOQ	lower limit of quantification
MedDRA	Medical Dictionary for Regulatory Activities
PD	pharmacodynamic
PFS	prefilled syringe
PK	pharmacokinetic
SAP	Statistical Analysis Plan
SC	subcutaneous

SD	standard deviation
TFLs	Tables, Figures, and Listings
$t_{1/2}$	half-life
$t_{\max}$	time of maximum observed concentration
$V_z/F$	apparent volume of distribution during the terminal phase after extra-vascular administration
WHO	World Health Organization

### 3. INTRODUCTION

This SAP has been developed after review of the Clinical Study Protocol (final version dated 31 May 2016).

This SAP describes the planned analysis of the safety, tolerability, pharmacokinetic (PK) and pharmacodynamic (PD) data from this study. A detailed description of the planned TFLs to be presented in the clinical study report (CSR) is provided in the accompanying TFL shell document.

The intent of this document is to provide guidance for the statistical and PK analyses of data. In general, the analyses are based on information from the protocol, unless they have been modified by agreement between Eli Lilly and Company and Covance Early Clinical (EC) Biometrics. A limited amount of information concerning this study (e.g., objectives, study design) is given to help the reader's interpretation. This SAP must be signed off prior to first subject administration for this study. When the SAP and TFL shells are agreed upon and finalized, they will serve as the template for this study's CSR.

This SAP supersedes the statistical considerations identified in the protocol; where considerations are substantially different, they will be so identified. If additional analyses are required to supplement the planned analyses described in this SAP, they may be performed and will be identified in the CSR. Any substantial deviations from this SAP will be agreed upon between Eli Lilly and Company and Covance EC Biometrics and identified in the CSR. Any minor deviations from the TFLs may not be documented in the CSR.

This SAP is written with consideration of the recommendations outlined in the International Council on Harmonisation (ICH) E9 Guideline entitled Guidance for Industry: Statistical Principles for Clinical Trials and the ICH E3 Guideline entitled Guidance for Industry: Structure and Content of Clinical Study Reports.

### 4. STUDY OBJECTIVES

#### 4.1 Primary Objective

- To determine the relative bioavailability of 240 mg LY2951742 after subcutaneous (SC) administration of LY2951742 solution as a manual prefilled syringe (PFS) (reference) or autoinjector (AI) (test).

#### 4.2 Secondary Objectives

- To assess plasma calcitonin gene-related peptide (CGRP) concentrations after SC administration of 240 mg LY2951742 solution as a PFS or AI.
- To assess the safety and tolerability of LY2951742 in healthy subjects after SC administration of 240 mg LY2951742 solution as a manual PFS or AI.

## 5. STUDY DESIGN

[figure not shown]
This will be a Phase 1, multi-center, open-label, 2-arm (PFS, AI), randomized, parallel group study where a single dose of 240 mg LY2951742 will be administered to healthy subjects.

Screening will occur up to 45 days prior to dosing with LY2951742.

Subjects will be admitted to the clinical research unit (CRU) on Day -1. Subjects will be randomized in a 1:1 ratio to 240 mg LY2951742 as a PFS (reference) or 240 mg LY2951742 as an AI (test). All doses will be administered in the morning of Day 1 as two 1-mL subcutaneous injections of 120 mg/mL solution of LY2951742. Subjects will be stratified to receive injections in the upper arm, abdomen, or thigh in each arm of the study, with similar numbers of subjects for each site of injection.

Subjects will remain resident at the CRU until the procedures scheduled at 24 hours postdose have been completed on Day 2, or longer at the discretion of the investigator. All subsequent procedures will be performed on an outpatient basis over a period of approximately 20 weeks (5 half-lives of LY2951742) after study drug administration, including an end-of-study visit (Day 141).

Figure 1.

Abbreviations: CRU = clinical research unit; D = day; PFS = prefilled syringe; SC = subcutaneous

## 6. TREATMENTS

The following is a list of the study treatment abbreviations that will be used in the TFLs.

Study Treatment Name	Treatment order in TFL
240 mg LY2951742 PFS	1
240 mg LY2951742 autoinjector	2

Abbreviations: PFS = prefilled syringe

## 7. SAMPLE SIZE JUSTIFICATION

Up to 160 subjects will be enrolled (80 in each arm). The number of subjects was determined on the basis of Study I5Q-MC-CGAO Part B interim data, a Phase 1 single-dose study evaluating 300 mg LY2951742 solution administered as a PFS. The percent coefficient of variation for LY2951742 maximum observed drug concentration ( $C_{max}$ ) and area under the concentration versus time curve from zero to infinity ( $AUC_{0-\infty}$ ) was approximately 35%. One-hundred sixty (160) subjects (80 per arm) will provide approximately 90% power to demonstrate that the 90% confidence interval (CI) of the ratio of geometric means between test and reference devices for the PK parameter falls within 0.8 to 1.25, assuming the true ratio is 0.95 and 12.5% of subjects will not contribute to the endpoint. Randomized and dosed subjects with insufficient collection of PK samples may be replaced at the discretion of the sponsor.

## 8. DEFINITION OF ANALYSIS POPULATIONS

The “Safety” population will consist of all subjects who received at least 1 dose of study drug, whether or not they completed all protocol requirements.

The “Pharmacokinetic” population will consist of all subjects who are compliant with dosing and have evaluable PK data.

The “Pharmacodynamic” population will consist of all subjects who are compliant with dosing and have evaluable PD data.

All protocol deviations that occur during the study will be considered for their severity/impact and will be taken into consideration when subjects are assigned to analysis populations.

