- d Unless otherwise specified, safety monitoring procedures throughout the study should be performed at approximately the same time of day (± 2 hours) as dosing was performed on Day 1 (except for procedures scheduled at screening and Day -1).
- e Each subject will receive a single dose of 240 mg LY2951742 in the morning, administered as 2×1 -mL (120 mg/mL) subcutaneous injections of solution formulation in either a manual prefilled syringe or an autoinjector device. Injection-site reactions after injection will be assessed as part of AE collection.
- f Complete physical examination to be performed at screening and at the final visit for each subject; directed physical examination only at other visits and as clinically indicated.
- g Height to be measured at screening only.
- h Vital signs include sitting blood pressure and pulse rate.
- i Additional urine drug screen and ethanol tests may be performed at the investigator's discretion.
- j Required for females of child-bearing potential only; however, pregnancy tests carried out in females of non-childbearing potential pending receipt of follicle-stimulating hormone results will not be considered a protocol deviation. Serum pregnancy test will be done on screening, and may be repeated using urine or serum test prior to admission to the clinical research unit and as clinically indicated.
- k When possible, PK samples on follow-up outpatient visit days should be collected at a time of day close to when dosing occurred on Day 1 (± 2 hours). PK sampling times are given as targets to be achieved within reasonable limits. The actual time of PK sampling should be recorded.
- l Baseline plasma CGRP sample will be taken on Day 1 prior to study drug injection.

3. Introduction

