10.3. Statistical Analyses

Statistical analysis of this study will be the responsibility of Eli Lilly and Company or its designee.

Pharmacokinetic and PD analyses will be conducted using subjects with evaluable PK and PD data. A subject is considered to be evaluable for PK and PD analysis if that subject is compliant with the dosing and PK and PD sampling scheme. Safety analyses will be conducted for all subjects who received at least 1 dose of study drug, whether or not they completed all protocol requirements.

Exploratory analyses of the data will be conducted as deemed appropriate. Study data may be combined with other studies for safety, PK, and/or PD analyses.

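### Does the SAP need a numerical rule for how much missed sampling removes a subject from the PK and PD populations?

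*SAP*

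**What the plan says.** SAP Section 8 defines two populations for concentration data. For PK the wording is "population will consist of all subjects who are compliant with dosing and have evaluable PK data". A matching rule covers the CGRP data and reads "population will consist of all subjects who are compliant with dosing and have evaluable PD data". The section then adds: "All protocol deviations that occur during the study will be considered for their severity/impact", and says this feeds into assignment to populations.

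Protocol 10.3 is fuller. It counts a subject as evaluable "if that subject is compliant with the dosing and PK and PD sampling scheme".

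Three other places bear on the point:

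- Protocol Section 2, Schedule of Activities, footnote k: "PK sampling times are given as targets to be achieved within reasonable limits".
- SAP Section 7, repeating Protocol 10.1: "Randomized and dosed subjects with insufficient collection of PK samples may be replaced at the discretion of the sponsor". The same paragraph assumes that "12.5% of subjects will not contribute to the endpoint".
- SAP Section 3 says the SAP supersedes the protocol's statistical considerations, but "where considerations are substantially different, they will be so identified". SAP Section 11 then reports no changes.

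**The concern.** The SAP governs the analysis and writes out only the dosing half of the protocol's definition. It leaves the word evaluable unexplained, and no document turns non-compliance or insufficient collection into a count, pattern or timing of missed samples. Two opposite readings then seem possible.

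- **Lenient.** Any dosed subject with a calculable parameter is in. Subjects who leave early have end-of-study procedures, including a last PK and CGRP sample, so a short AUC(0-tlast) could enter the ANOVA beside 20-week areas.
- **Strict.** Any missed sample puts a subject out. That would shrink the population that also feeds the primary Cmax and AUC(0-inf) comparisons.

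The study is open label, and SAP 8 does not say when populations are fixed. On its face, the choice between the readings could be made with device and concentrations in view.

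**Working it through.** **1. The plan's own figure.** Inputs from SAP 7: 80 per arm, 12.5% not contributing, CV 35%, true ratio 0.95, limits 0.80 to 1.25.

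- Evaluable per arm: 80 × (1 − 0.125) = 70.
- Log-scale SD: √ln(1 + 0.35²) = 0.340.
- Standard error: 0.340 × √(2/70) = 0.0575.
- Distances to the limits: ln(0.95/0.80) = 0.172 and ln(1.25/0.95) = 0.274. The t quantile (0.95, 138 df) is 1.656.
- Power ≈ Φ(0.172/0.0575 − 1.656) + Φ(0.274/0.0575 − 1.656) − 1 ≈ 0.909 + 0.999 − 1 = 0.908. Exact integration gives 0.907.

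The stated figure of about 90% reproduces with every non-contributor excluded.

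**2. Which definition applies.** SAP 3 promises to flag substantial differences from the protocol, and SAP 11 flags none. Dropping the sampling condition would be a substantial difference, so the consistent reading is that Protocol 10.3 still defines evaluable.

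**3. What already limits judgement.**

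| Rule | Place |
|---|---|
| Deviations weighed by severity and impact | SAP 8 |
| Sampling times are targets | Protocol 2, footnote k |
| Actual sampling times used | SAP 9.3.1.1 |
| AUC needs three consecutive quantifiable values, at least one after Cmax | SAP 9.3.1.1 |
| Half-life needs a reliable estimate from at least 3 points; flagged if the window is under 2 half-lives | SAP 9.3.1.1 |
| AUC(0-inf) flagged above 20% extrapolation; any exclusion footnoted | SAP 9.3.1.1 |
| Excluded subjects highlighted in listings | SAP 9.1 |

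SAP 9.4.1 carries the 9.3.1.1 rules to CGRP where appropriate.

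**4. Lenient reading, galcanezumab AUC(0-tlast).** The assumptions are:

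- A one-compartment curve with tmax 10 days and half-life 27.5 days, inside the protocol's 7–14 and 25–30 days.
- 12.5% × 160 = 20 subjects leave at random, without regard to arm. Their last visit is uniform over scheduled visits from a start day to Day 113.
- The 0.80–1.25 limits and 35% CV are borrowed for this endpoint; the documents give them only for the sample size.

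The area collected by time t is F(t) = 1 − (ka·e^(−ke·t) − ke·e^(−ka·t))/(ka − ke), with ke = ln 2/27.5 and ka = 0.258 per day. A leaver's area is scaled by F(t)/F(140).

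| Leaving starts | Power, short areas kept |
|---|---|
| Day 15 | 82.0% |
| Day 22 | 87.4% |
| Day 29 | 90.5% |
| Day 57 | 93.1% |
| Leavers excluded | 90.7% |

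The mean ratio stays at 0.950 and interval coverage at 90% in every row. Short areas add noise to both arms alike and do not shift the comparison. Observed Cmax is largely untouched, because these subjects leave at or after the 7–14 day peak.

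**5. Strict reading, primary endpoints.** The schedule has 15 outpatient sampling visits. With an assumed independent miss rate p per visit, the share with every sample is (1 − p)^15.

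- The 12.5% allowance is used up at p = 1 − 0.875^(1/15) = 0.9%.
- At p = 1%, 2% and 3%, 69, 59 and 51 per arm remain, with power 90%, 86% and 81%.

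These losses arise only if a single missed sample removes a subject. That cannot be squared with weighing deviations by impact in SAP 8, or with treating sampling times as targets. The figures also ignore the replacement rule.

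**The case for a change.** The best case for a change is that the rules in SAP 9.3.1.1 decide whether a parameter can be calculated, not whether a subject belongs to a population, and that the 20% flag does not by itself remove anyone. AUC(0-tlast) and the CGRP area have no extrapolation flag. The protocol's reason for an open-label design, that PK is objective, protects the measurement but not the choice of subjects. A few sentences in SAP 8 would close the gap at almost no cost.

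The description is accurate: no subject-level threshold exists, and neither document fixes when populations are assigned. A sentence tying SAP 8 to Protocol 10.3 would be tidier. It would not alter a result obtained by following the documents as they stand.

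A numerical cutoff is not clearly an improvement either. Take Day 85 as the earliest acceptable last visit. On the assumed curves it is the first visit with under 20% extrapolated across the whole range (10–17%, against 15–23% at Day 71). But that criterion belongs to AUC(0-inf). It would be borrowed for AUC(0-tlast), and for CGRP, whose curve the documents do not give. At the central values Day 71 already passes, at 19.0%. If leaving starts only at Day 57, the cutoff gives lower power than keeping everyone (92.3% against 93.1%). If leaving is related to exposure, excluding those subjects could itself move the ratio.

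**Conclusion.** No change to the plan. This is an unwritten detail, not a rule that yields a wrong answer. The protocol's definition of evaluable carries over, and the SAP's impact-based handling of deviations, parameter minimums and reporting of exclusions lead a competent analyst to a sensible population.

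Excluding all of the assumed 12.5% gives 90.7% power, as planned. Keeping them causes no bias. In the worst case examined it costs about 9 points of power (90.7% to 82.0%), on a supportive endpoint and with dropout starting at Day 15. The 81–86% figures for the primary endpoints need a one-miss-and-out rule that the text contradicts.

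This rests on dropout unrelated to device and on an assumed one-compartment galcanezumab curve. Dropout timing and miss rates are also assumed. The effect on the CGRP area cannot be sized, because the documents give no CGRP profile, variability or acceptance limits.
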